1.6. SECONDARY OUTCOMES

1.6.1. Secondary Efficacy Outcomes

Secondary Outcome 1. The numbers of days of opioid treatment from the first weaning dose to cessation of opioid with a rapid and slow-wean interventions among infants treated with morphine.

Secondary Outcome 2. The numbers of days of opioid treatment from the first weaning dose to cessation of opioid with a rapid and slow-wean interventions among infants treated with methadone.

Secondary Outcome 3. The proportions of infants in the rapid and slow-wean intervention arms who have an escalation or resumption of opioid medication during weaning.

Secondary Outcome 4. The total amounts of opioid from the first weaning dose to cessation of opioid among infants in the rapid and slow-wean intervention arms.

Secondary Outcome 5. The proportion of infants who experience initiation and/or escalation of second-line or third-line drugs to treat NOWS signs from the first weaning dose to cessation of opioid in the rapid-wean and slow-wean intervention arms.

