5.1.2. Secondary Outcomes

Secondary Efficacy Outcomes.

Secondary Outcome 1: Compare the numbers of days of opioid treatment from the first weaning dose to cessation of opioid with a rapid- and slow-wean intervention among infants treated with morphine.

Secondary Outcome 2: Compare the numbers of days of opioid treatment from the first weaning dose to cessation of opioid with a rapid- and slow-wean intervention among infants treated with methadone.

Secondary Outcome 3: Compare the proportions of infants in the rapid- and slow-wean intervention arms who have an escalation or resumption of opioid during weaning.

Secondary Outcome 4: Compare the total amounts of opioid from the first weaning dose to cessation of opioid among infants in the rapid- and slow-wean intervention arms.

Secondary Outcome 5: Compare the proportion of infants who experience initiation and/or escalation of second- or-third line drugs to treat NOWS signs from the first weaning dose to cessation of opioid in the rapid- and slow-wean intervention arms.

Secondary Safety Outcome.

Secondary Outcome 6: Compare the proportion of infants in each intervention arm with safety outcomes of seizures (clinical or EEG), excessive stool output, respiratory disturbances, and feeding tolerance.

Other Secondary Outcomes.

Secondary Outcome 7: Compare the proportion of infants in each treatment intervention arm with an atypical neurobehavioral profile prior to discharge on the NICU Network Neurobehavioral Scale (NNNS).

Secondary Outcome 8: Compare the lengths of hospital stay for each treatment intervention arm.

Secondary Outcome 9: Determine assessments of maternal well-being and maternal-infant attachment in each intervention arm.

Secondary Outcome 10: Assessments of growth in each intervention arm.

Secondary Outcome 11: Assessment of infant wellness after discharge and until 24 months of age in each intervention arm.

Secondary Outcome 12: Assessment of infant development to 24 months of age in each intervention arm.

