5.1.5. Analyses of Secondary Outcomes

We will use the same approach described in the primary outcome analysis to compare the number of days of opioid treatment with only infants receiving morphine as the primary pharmacological treatment for NOWS (Secondary Outcome 1). We will use this same approach to compare the number of days of opioid treatment using only infants receiving methadone as the primary pharmacological treatment for NOWS (Secondary Outcome 2).

We will use adjusted logistic regression models to provide an odds ratio (OR) and 95% Confidence Intervals (CI) for binary secondary outcomes measured only once. These outcomes will include:

- the proportion of infants by intervention arms that escalate or resume opioid medication during weaning,
- for the proportion of infants by intervention arms with an atypical neurobehavioral profile (**Profile 5, Figure 1**),
- the proportion of infants who receive an escalation of a second-line or third-line drug to treat NOWS signs from the first weaning dose to cessation of opioid.

Title: Pragmatic, Randomized, Blinded Trial to Shorten Pharmacologic Treatment of Newborns with Neonatal Opioid Withdrawal Syndrome (NOWS)

Sponsor: National Institutes of Health

We will adjust these models for the stratification variable (hospital), covariates of maternal treatment and stabilization dose, and baseline variables that may differ between groups by chance. We define the covariates that we may adjust for earlier in this section in the paragraph on other collected data.

We will analyze the secondary outcome of the total opioid exposure from the first weaning dose to cessation of opioid in a similar manner as the primary outcome. We will use a regression model that will include: a fixed treatment effect (intervention arms) and adjustment for the stratifying variable, covariates of maternal treatment and stabilization dose, and baseline variables that may differ between groups by chance as fixed effects. We will include hospital (site) as a random effect. The primary test of interest will be the F-test of the intervention arm effect, and we will report the treatment difference along with 95% CI.

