APPENDIX 10. PLACEBO DOSE UTILIZATION TO MAINTAIN THE BLIND IN THE RAPID-WEAN INTERVENTION

All infants that are randomized to the rapid-wean intervention will need to complete three placebo dose levels to maintain the blind (Appendices 4-7). Placebo administration only occurs after the infant has weaned from the 25% of stabilization dose level. We will consider a placebo dose level complete if the infant meets the following two criteria:

- 1) The infant tolerates the placebo without NOWS signs prompting a resumption of opioid.
- 2) The clinical team starts the next dose level in the intervention (i.e., the clinical team orders “wean opioid.”). If during a placebo dose the clinical team orders “escalate opioid”, then we will not consider the placebo dose complete. The clinical team needs to repeat a placebo dose that is not complete.

For infants who experience the same number of escalations or resumptions, placebo use in the rapid-wean intervention will result in study drug discontinuation after the same number of study steps as infants in the slow-wean intervention. Examples below demonstrate how placebo use in the rapid-wean intervention will maintain the blind (infant A). These examples include an infant without escalations (example A), an infant who has two escalations prior to reaching placebo (example B), an infant with one escalation that occurs during a placebo dose level (example C), an infant with two escalations: one that occurs during an opioid dose level and one that occurs during a placebo dose level (example D), and an infant with two escalations that both occur during the placebo levels (example E). For each example, we show an infant randomized to the slow-wean intervention with an identical number of escalations or resumptions of opioid (infant B).

We present the examples in terms of steps (not dose levels) to illustrate that there will be more study steps than dose levels when there are escalations of the opioid. In the examples, every infant randomized to the rapid-wean intervention needs to complete three placebo dose levels. We will consider placebo dose levels incomplete if opioid resumption interrupts them. The three placebo dose levels do not need to occur consecutively. For the research team to consider a placebo level complete, it needs to lead to a successful wean to another placebo level or off study drug.

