Title: Pragmatic, Randomized, Blinded Trial to Shorten Pharmacologic Treatment of Newborns with Neonatal Opioid Withdrawal Syndrome (NOWS)

Sponsor: National Institutes of Health

A			B		
	Infant A	Infant B		Infant A	Infant B
	Rapid wean:	Slow wean:		Rapid wean:	Slow wean:
	15 % of stabilization dose	10 % of stabilization dose		15 % of stabilization dose	10 % of stabilization dose
Stabilization Dose	100	100	Stabilization Dose	100	100
Step 1	85	90	Step 1	85	90
Step 2	70	80	Step 2	70	80
Step 3	55	70	Step 3	85	90
Step 4	40	60	Step 4	70	80
Step 5	25	50	Step 5	85	90
Step 6	Placebo*	40	Step 6	70	80
Step 7	Placebo*	30	Step 7	55	70
Step 8	Placebo*	20	Step 8	40	60
Key:			Step 9	25	50
Placebo Step			Step 10	Placebo*	40
Dose Medication is discontinued			Step 11	Placebo*	30
			Step 12	Placebo*	20
			Key:		
			Placebo Step		
			Dose Medication is discontinued		
			Escalation		

A. No Escalations. Infant A stops opioid at step 5. Infant B continues opioid until step 8. To maintain the blind, infant A receives placebo for steps 6-8. Both infants stop receiving “opioid/study drug” at step 8. **B. Two Escalations during Opioid Steps.** Both infants escalate at steps 3 and 5. Infant A discontinues opioid at step 9. Infant B discontinues opioid at step 12. Infant A receives 3 steps of placebo (10-12) to preserve blind. Both infants discontinue “study drug” at step 12.

C			D		
	Infant A	Infant B		Infant A	Infant B
	Rapid wean:	Slow wean:		Rapid wean:	Slow wean:
	15 % of stabilization dose	10 % of stabilization dose		15 % of stabilization dose	10 % of stabilization dose
Stabilization Dose	100	100	Stabilization Dose	100	100
Step 1	85	90	Step 1	85	90
Step 2	70	80	Step 2	70	80
Step 3	55	70	Step 3	55	70
Step 4	40	60	Step 4	40	60
Step 5	25	50	Step 5	25	50
Step 6	Placebo*	40	Step 6	40	60
Step 7	Placebo*	30	Step 7	25	50
Step 8	25	40	Step 8	Placebo*	40
Step 9	Placebo*	30	Step 9	25	50
Step 10	Placebo*	20	Step 10	Placebo*	40
Key:			Key:		
Placebo Step			Placebo Step		
Dose Medication is discontinued			Dose Medication is discontinued		
Escalation			Escalation		
Incompleted Placebo Step			Incompleted Placebo Step		
Escalation from Previous Dose and Discontinue			Escalation from Previous Dose and Discontinue		

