H₀: The rate of escalation or resumption of opioid during weaning will not differ between rapid- and slow-wean treatment regardless of medication used.

H_a: The rate of escalation or resumption of opioid during weaning will differ between rapidand slow-wean treatment regardless of medication used.

5) **Research Objective 5**: To compare the total amounts of opioid from the first weaning dose to cessation of opioid among infants in rapid- and slow-wean intervention arms. Statistical Hypothesis 4: The total amounts of opioid used from the first weaning dose to cessation of opioid will be lower in rapid-wean group that in slow-wean group regardless of medication used.

H₀: Total amounts of opioid used from the first weaning dose to cessation will not differ between rapid- and slow-wean treatment regardless of medication used.

H_a: Total amounts of opioid used from the first weaning dose to cessation will differ between rapid- and slow-wean treatment regardless of medication used.

6) **Research Objective 6**: To compare the proportion of infants who experience initiation and/or escalation of second-or-third line drugs to treat NOWS signs from the first weaning dose to cessation of opioid in the rapid- and slow-wean intervention arms.

H₀: Proportion of infants who experience initiation and/or escalation of second-or-third line drugs to treat NOWS signs from the first weaning dose to cessation will not differ between rapid- and slow-wean treatment regardless of medication used.

H_a: Proportion of infants who experience initiation and/or escalation of second-or-third line drugs to treat NOWS signs from the first weaning dose to cessation will differ between rapid-and slow-wean treatment regardless of medication used.

Additionally, for this objective a descriptive table with second-or-third line drugs to treat NOWS signs initiated before start of study drug will be provided.

Safety secondary outcome, Table 2

- 7) **Research Objective 7:** To compare the proportion of infants in each intervention arm with any safety outcome (seizure, excessive stool, respiratory disturbance, and/or feeding intolerance).
 - A) **Objective 7.a:** To compare the proportion of infants in each intervention arm with seizures (clinical or EEG)
 - B) **Objective 7.b**: To compare the proportion of infants in each intervention arm with excessive stool output
 - C) **Objective 7.c**: To compare the proportion of infants in each intervention arm with respiratory disturbances

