4.1 Modeling Process

For the primary outcome (H1), linear mixed model with site as random effect and intervention as a fixed effect will be used.

For safety outcomes, binomial proportions and their corresponding 95% CI by intervention arm for seizure (clinical and EEG), excessive stool output, respiratory disturbances, and feeding intolerance will be reported. Chi-square/Fisher exact tests will be used to compare between the intervention arms. If we end up with a very small number of adverse events and severe adverse events, analysis of these measures will be descriptive only.

For the secondary linear outcomes (H2, H3, H5 & H12d), linear mixed model with site as random effect will be used. For secondary binary outcomes (H4, H6), generalized linear mixed model with site as random effect will be used. For count outcomes (H12a-12c), generalized linear mixed models using either Poisson or negative binomial distribution and site as random effect will be used. Intervention will be included in the models as a fixed effect. Secondary outcome models will be adjusted for breastfeeding status, maternal treatment, and stabilization dose.

Hypotheses H9 – H11 will be analyzed in a similar manner to H2. For the PROMIS model (H10), we will adjust for 1-month after discharge and if mother is the primary care giver as fixed effect covariates.

Hypothesis H8 will be analyzed using latent profile analysis as specified in Liu et al. (2). Model fit indices and likelihood ratio tests will inform the determination for the most-appropriate number of classes.

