6.3 Secondary Outcomes

Secondary outcomes that will be considered during initial analysis will include but not limited to:

• Number of days on morphine from first weaning dose to cessation of opioid for slow- and rapid-wean groups (H2)

- Number of days on methadone from first weaning dose to cessation of opioid for slowand rapid-wean groups (H3)
- Escalation or resumption of opioid during treatment (Y/N scenario)) (H4)
- Total amount of opioid from first weaning dose to cessation of opioid for non-withdrawn infants (H5)
- Initiation and/or escalation of second- or third- line drugs to treat NOWS signs from the first weaning dose to cessation (H6)
- Atypical neurobehavioral profile prior to discharge using the NICU Network Neurobehavioral Scale (NNNS)(H8)
- Length of hospital stay (H9)
- Maternal well-being measured using PROMIS, one month post discharge and at 24-month follow-up visit (H10)
- Maternal-infant attachment measured using MPAQ total scores, one month post discharge (H10)
 - o Maternal well-being
 - o maternal-infant attachment
- Infant growth (H11)
 - o Weight, height, head circumference at 24-month follow-up visit
- Infant wellness after discharge and initial 24 months of age looking at ER and acute care facility visits over time (Y/N for time (1-4)) (H12)
- BISTEA consists of two multi-item scales, a problem scale (31 items) and competence scale (11 items), with high score on the problem scale or a low score on the competence scale being less favorable. (H12). These scores will be converted to percentiles based on BITSEA Examiner's Manual (BITSEA ph2 Manual MapiTrust.pdf)
- Infant development to 24 months of age (H13)
 - o Bayley cognitive, language, and motor performed by a developmental specialist.

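### The adjunct-drug outcome (H6) stops counting at the last opioid dose, which at matched escalations comes one to three dose levels before the end of study drug in the rapid arm only

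*SAP*

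**What the plan says.** The on-opioid window for H6 is stated consistently. SAP 2.2.1 (Objective 6) counts "initiation and/or escalation of second-or-third line drugs to treat NOWS signs from the first weaning dose to cessation of opioid". Protocol 1.6.1 has "initiation and/or escalation of second-line or third-line drugs to treat NOWS signs from the first weaning dose to cessation of opioid", and Protocol 5.1.2 repeats it. SAP 6.3 lists the same outcome without saying what ceases, but Objective 6 settles that it is the opioid.

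The protocol separates the end of opioid from the end of study drug. In Appendix 10, example A (no escalations), "Infant A stops opioid at step 5. Infant B continues opioid until step 8"; the rapid infant takes placebo at steps 6 to 8 and both stop study drug at step 8. The equal number of steps is promised only "For infants who experience the same number of escalations or resumptions". In the slow arm every study-drug level contains opioid (Protocol Table 4), so the two end points coincide there.

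Protocol 4.2.8 lets clinical teams start second- and third-line drugs after randomization and adjust them during the intervention. On the model, SAP 4.1 says: "For secondary binary outcomes (H4, H6), generalized linear mixed model with site as random effect will be used". No offset or other allowance for window length is given.

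**The concern.** The assigned arm helps to set how long each infant is observed for H6. A blinded team that adds an adjunct at step 7 in example A produces a counted event in the slow arm. In the rapid arm the same action is not counted unless opioid is later resumed. The uncounted period is also the time just after opioid has been withdrawn.

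H6 is the planned comparison of whether faster weaning moves treatment onto adjunct drugs. Neither the opioid escalation outcome (H4) nor the safety outcomes count adjuncts. A lower rapid-arm proportion could therefore be reported as less adjunct use when part or all of it comes from the shorter window.

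**Working it through.** **1. Window length at matched escalations** (Protocol Tables 4 and 5, Appendix 10). The plan's own figure of three placebo levels reproduces.

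| Pattern | Last opioid step, rapid | Last opioid step, slow (= end of study drug) | Gap |
|---|---|---|---|
| A, no escalation | 5 | 8 | 3 |
| B, D | 9 | 12 | 3 |
| C | 8 | 10 | 2 |
| E, Table 5 | 10 | 12 | 2 |

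Applying the same rules to other patterns of up to three escalations gives gaps of 1, 2 or 3, never more, with equal total steps each time. A gap of 1 arises when the third placebo level fails: the rapid infant's last opioid step is then 9 of 10. The gap is 0 only if opioid is restarted after study drug has ended (Protocol 4.2.6, Post Intervention). Three levels last 3 × 24 h = 3 days, or 3 × 36 h = 4.5 days if the 12-hour protocol period is used in full, and less if weaning is faster.

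**2. Illustration with no true difference.** Assumptions, not in the documents: adjunct probability p over the study-drug period, the same constant per-step hazard in both arms, and a fraction r of placebo-phase events brought back into the window by later opioid resumption. With k the last opioid step in the rapid arm and m the last study-drug step:

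q = 1 − (1 − p)^(k/m); recorded rapid proportion q_r = q + r(p − q); OR = odds(q_r) / odds(p).

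Example A, p = 0.20:
- r = 0: q = 1 − 0.8^(5/8) = 0.130; OR = 0.1497/0.25 = 0.60
- r = 0.5: q_r = 0.165; OR 0.79
- r = 1: q_r = 0.200; OR 1.00

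Examples B to E at p = 0.20 give OR 0.73 to 0.82 at r = 0 and 0.86 to 0.91 at r = 0.5.

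Chance of a nominal p < 0.05 in example A, at 151 per arm (half the 302 target in SAP 3.4; unadjusted chi-square, exact binomial enumeration):

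| Assumed rate | r = 0 | r = 0.5 | r = 1 |
|---|---|---|---|
| 5% | 12% | 6.5% | 5% |
| 10% | 20% | 8% | 5% |
| 20% | 37% | 12% | 5% |

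At 20%, 0.20 × 151 = 30.2 rapid-arm events are expected. At r = 0 the window records 19.7, leaving 10.5 uncounted.

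**3. Unmatched escalations.** Take the per-step hazard that gives 20% over 8 steps, and compare a rapid infant who escalates with a slow infant who does not (window 8 steps):
- rapid C, 8 steps: OR 1.00
- rapid B or D, 9 steps: 1 − 0.8^(9/8) = 0.222; OR 1.14
- rapid E, 10 steps: 1 − 0.8^(10/8) = 0.243; OR 1.29

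**4. The alternative window has its own tilt.** Count both arms to the last study-drug dose and let the hazard on placebo be h times that on opioid. In example A the rapid proportion is 1 − 0.8^((5 + 3h)/8). For h = 1, 1.5 and 2 this is 0.200, 0.233 and 0.264, with OR 1.00, 1.21 and 1.44. The slow arm's off-opioid time falls outside this window.

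**The case against.** The on-opioid window is prespecified, matches the interval of the primary outcome, and answers a coherent question: adjunct use while opioid is being weaned. Earlier opioid cessation is the intended effect. That stands, and it is why the window should be kept and not replaced.

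Recapture is the protocol's own route. Protocol 4.2.6 makes escalation of study drug the response to signs that need more drug, and on placebo that restarts opioid and reopens the window. Infants also reach placebo only after tolerating the 25% level, so a constant hazard is unsupported. Both points stand. They limit the size, but because adjuncts are separately permitted throughout, full recapture is not assured.

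A reader might infer that the rule biases H6 towards rapid wean overall. The documents do not support that. Protocol 3.3.4 presumes more recurrence with larger decrements, and step 3 of the working shows that more rapid-arm escalations can equalise or lengthen its window. A reader might also take the 37% as an estimate of the false-positive rate. It is the no-recapture, no-escalation case at an assumed 20%, with a simpler test than the planned adjusted mixed model, and at a target that preceded the decision to end enrolment.

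Protocol 5.1.5 describes the analysis as "the proportion of infants who receive an escalation of a second-line or third-line drug to treat NOWS signs", omitting initiation. That is a clerical slip which the SAP already corrects. Nor does any section stop H6 at exit from the intervention.

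**Conclusion.** The concern holds as a minor point about measurement and interpretation. At matched escalations the H6 window is one to three dose levels shorter in the rapid arm, nothing in the model allows for this, and the result can favour rapid wean. That part follows from the protocol's own rules.

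The net direction and size across the trial cannot be derived. Three inputs are missing: the adjunct rate during weaning, the share recaptured by opioid resumption, and escalation rates by arm. The nearest adjunct figure, 223 of 698 treated infants (32%, Protocol Appendix 2), covers the whole treatment course. The odds ratios of 0.60 to 1.00 rest on an assumed 20% rate, a constant hazard and no escalations.

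H6 is secondary, and SAP 6.4.4 treats every analysis other than the primary as exploratory. The primary conclusion is unaffected.

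**What to change.** In SAP Objective 6 and 6.3, keep the on-opioid window and add one labelled sensitivity analysis of H6 with the same end point in both arms: from first weaning dose to last dose of blinded study drug, placebo levels included, or to discharge if adjunct use was recorded that far. Report the two results side by side by arm. State that a lower on-opioid proportion alone will not be read as less adjunct use with rapid wean. If H6 has already been analysed (SAP 3.7 expected the first phase to start in April 2024), the label should say so.

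The cost is one derived variable and one extra analysis. Protocol Table 3 lists second- and third-line drugs under intervention data collection, but how far recording ran should be confirmed first. The study-drug window includes off-opioid time in the rapid arm only, so it can tilt against rapid wean, and it matches in steps only when escalations match. Running to discharge would add the slow arm's off-opioid observation and reduce that tilt.

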5.1.3. Other Collected Data

Initial descriptive analyses will include weaning intervention group characteristics. We will collect data to characterize the following.

- Stratification data
- Hospital variables: participation in ESC
- Maternal variables (e.g., socioeconomic status, obstetric complications, opioid medication, medication assisted treatment program, non-opioid drugs, cigarettes, alcohol, selective serotonin reuptake inhibitors, and psychiatric diagnoses)
- Infant demographics at birth (e.g., gestational age, birth weight, sex, multiples, growth parameters, out-born, and location of care)
- Characteristics of NOWS treatment (e.g., stabilization dose, age at stabilization, use of adjunctive drugs to the primary NOWS drug treatment)
- Infant characteristics at the start of the intervention (e.g., weight, postnatal age) and when medically ready for discharge per the hospital standard.

We will include the stratification variable (hospital) in regression modeling as a random effect, and we will include stabilization dose and maternal treatment as covariates. With respect to maternal treatment, it will be a categorical variable with four categories:

- 1) Methadone use
- 2) Buprenorphine \pm naloxone
- 3) Prescribed opioids other than methadone and buprenorphine \pm naloxone
- 4) Non-prescribed opioids

There will be some mixing among these four groups; therefore, we will use the following rules to classify infants:

- If methadone is used with other opioids, classify as methadone.
- If buprenorphine is used with other opioids, classify as buprenorphine \pm naloxone.
- If methadone is used with buprenorphine, classify based on which drug has been in use for a longer time interval.

Depending on the descriptive comparisons across weaning intervention groups, we may add other variables to the regression models such as medication assisted treatment programs. If the difference of a variable across the weaning intervention is statistically significant at a two-sided alpha of 0.05, then we may include the variable as a covariate in the regression models. Beyond the significant difference, we will consider other factors, such as the type of analysis, correlation with other variables in the model, and trial subcommittee discussion about the nature of the potential covariate.

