3.4 Sample Size

The projected effect size is a 2.0-day difference in the duration of opioid treatment between infants randomized to a rapid-wean intervention and infants randomized to a slow-wean intervention. The sample size was derived by using results from a recently completed trial comparing morphine-treated infants and methadone-treated infants in which the standard

deviation was 6.9 days for the morphine-treated infants and 8.0 days for methadone-treated infants (see protocol for more details). A standard deviation of 6.9 days was used to derive the sample size, anticipating that more infants will be treated with morphine. However, the primary analysis compares treatment regardless of drug used, and sample size was calculated irrespective of the proportion of infants treated with morphine or methadone.

The study will have two intervention arms (rapid-wean and slow-wean) with 251 morphine/methadone treated infants per intervention arm, for a total of 502 morphine/methadone treated infants. This will achieve 90% power to reject the null hypothesis with a significance level of 0.05 using a two-sided two-sample t-test. The null hypothesis will be morphine or methadone treated infants in both arms will have equal means when the population difference in the duration of opioid treatment is 2.0 days with a standard deviation of 6.9 days. Sample size recalculation was performed in July 2022, using a standard deviation of 6.2 based on data from enrolled infants up to June 2022. It was determined that a sample size of 404 is needed to reach 90% power to reject the null hypothesis with a significant level of 0.05 using a two-sided two-sample t-test, and 302 to reach 80% power. We chose this latter number as our target enrollment.

Subsequently, given continued enrollment challenges faced by this trial, the DSMC and NICHD decided to terminate the trial after December 31, 2023.

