 μ_i = expected value of outcome y_i

 β_0 = intercept, the expected mean number of treatment days when all covariates = 0

 β_1 = Intervention effect of fast vs slow wean interventions

 $\beta_2, \beta_3, \beta_4$ = effect of maternal treatment, compare to no treatment

 β_5 = effect of stabilization dose

 β_5 = effect of breastfeeding

 β_i = effect of the jth covariate added to the model

For normal outcomes, g(.) is the identity link function.

For binary outcomes, g(.) is the logit link function and we will assume that y_i follows Bernoulli distribution. Alternatively, we can follow Zou et al. (2003) and use the natural log function, and we will assume that y_i follows Poisson or negative binomial distribution. Decision will be based on manuscript writing team, if they prefer to report risks vs odd ratios.

For count outcomes, g(.) is the natural log function, and we will assume that y_i either follows Poisson or negative binomial distribution.

All hypothesis tests will be performed using a two-sided significance level of 0.05. Unless otherwise specified, results for each type regression performed will include the following:

- Normal regression
 - Unadjusted
 - Mean (and 95% confidence intervals (CI)) of the outcome in each treatment group.
 - Mean difference (and 95% CI) of the outcome between treatment groups.
 - Adjusted using pre-specified covariates.
 - Mean (and 95% CI) of the outcome in each treatment group.
 - Mean difference (and 95% CI and p-value) of the outcome between treatment groups.
- Logit Binomial regression
 - Unadjusted
 - Rate (and 95% CI) of the outcome in each treatment group
 - Odds Ratios (and 95% CI) of the outcome between treatment groups
 - Adjusted using pre-specified covariates.
 - Rate (and 95% CI) of the outcome in each treatment group
 - Odds Ratios (and 95% CI and p-value) of the outcome between treatment groups.
- Log-Binomial or Poisson regression
 - Unadjusted
 - Risk (and 95% CI) of the outcome in each treatment group
 - Relative risk (and 95% CI and p-value) of the outcome between treatment groups
 - Adjusted using pre-specified covariates.
 - Risk (and 95% CI) of the outcome in each treatment group
 - Relative risk (and 95% CI and p-value) of the outcome between treatment groups.
- Poisson or negative binomial regression
 - Unadjusted
 - Rate (and 95% CI) of the outcome in each treatment group
 - Relative rate (and 95% CI and p-value) of the outcome between treatment groups

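### The H6 model does not prespecify second-/third-line drug use before weaning, and the planned output does not separate initiation from escalation; the test stays valid, but power and readability may be lost

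*SAP*

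**What the plan says.** **Endpoint.** SAP 2.2.1 and 6.3 define H6 as a single proportion: infants with initiation and/or escalation of a second- or third-line drug between the first weaning dose and opioid cessation. Protocol 1.6.1 and 5.1.2 agree. Protocol 5.1.5, where the logistic model is described, names escalation only.

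**Model.** SAP 4.1: "For secondary binary outcomes (H4, H6), generalized linear mixed model with site as random effect will be used". The fixed covariates in SAP 4.1, 6.4.1 and 6.4.3 are breastfeeding, maternal treatment and stabilization dose. The model formula in SAP 6.4.1 leaves a slot for added covariates but does not name any.

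**Prior use.** Protocol 4.2.6 lets hospitals start these drugs before randomization and lists their use among the data collected. Protocol 5.1.3 lists "use of adjunctive drugs to the primary NOWS drug treatment" among the treatment characteristics to be described. For H6 itself the SAP adds that "a descriptive table with second-or-third line drugs to treat NOWS signs initiated before start of study drug will be provided".

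**Route into the model.** SAP 6.4.3 allows further adjustment in secondary analyses if sample size permits and if a critical covariate is imbalanced both clinically and statistically. Protocol 5.1.3 has a similar rule based on a 0.05 test. Protocol 5.1.5 is looser and mentions baseline variables that happen to differ by chance.

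**The concern.** An infant on no second- or third-line drug at the first weaning dose can have only one kind of first H6 event, an initiation. An infant already on one can have that drug escalated or another added. Prior use is therefore the nearest thing H6 has to a baseline value. The SAP ties it to this objective through the table but leaves it out of the model. For PROMIS, by contrast, the SAP adjusts the 24-month score for the 1-month score.

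Two separate things are at stake. One is efficiency, since a prognostic baseline variable that is already collected may go unused. The other is interpretation. H6 bears on whether rapid weaning replaces opioid with other drugs, and a pooled rate does not show whether a difference comes from new starts or from increases in treatment already under way.

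**Working it through.** **1. The plan's own figures.** No sample size or power is stated for H6. Those for the primary outcome use a 2.0-day difference and two-sided alpha of 0.05, with SD 6.9 originally and later "using a standard deviation of 6.2 based on data from enrolled infants up to June 2022". With n per arm = 2·SD²·(1.960 + z)²/2.0², where z is 1.282 for 90% power and 0.842 for 80%:
- SD 6.9, 90%: 250.1, so 251 per arm, 502 in total.
- SD 6.2, 90%: 201.95, so 202 per arm, 404 in total.
- SD 6.2, 80%: 150.9, so 151 per arm, 302 in total.

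All three match SAP 3.4. The target of 302 is used below. The SAP does not give the number enrolled at closure.

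**2. Assumptions for H6 (not in the documents).** Treatment odds ratio 2; H6 rate in the slow-wean arm p0 = 10%, 20% or 30%; prior use q = 10%, 20% or 32%; odds ratio of prior use on H6 from 0.2 to 10; no dropout. The 32% is 223/698 from protocol Appendix 2. It counts secondary medication at any time, so it is only an upper guide to use before weaning. Random site and the other covariates are left out.

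**3. Method.** Find the intercept a from (1−q)·expit(a) + q·expit(a + ln ORz) = p0, where ORz is the covariate odds ratio. Adding ln 2 to both terms gives p1.
- Without the covariate: effect = ln of the marginal odds ratio; SE = √[1/(151·p0(1−p0)) + 1/(151·p1(1−p1))].
- With it: effect = ln 2; SE from the inverse information matrix of the logistic model with arm and prior use.
- Power = Φ(effect/SE − 1.96).

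**4. One case in full** (q = 32%, p0 = 20%, ORz = 5). Slow-wean risks are 11.2% without and 38.7% with prior use, and p1 = 31.6%.
- Without: marginal odds ratio 1.84, SE 0.268, power Φ(2.28 − 1.96) = 62.6%.
- With: conditional odds ratio 2.00, SE 0.287, power Φ(2.42 − 1.96) = 67.6%.
- Simulation (4,000 trials): 63.4% and 68.4%.

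The SE of the log odds ratio rises. Power improves because the conditional effect is further from zero.

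**5. Range at N = 302**

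| Covariate OR | Power gain (points) | Fall in risk-difference variance |
|---|---|---|
| 1 | 0 | 0% |
| 0.5 | 0.1–0.8 | 0.4–2.2% |
| 2 | 0.3–0.9 | 0.8–2.5% |
| 0.2 | 0.4–3.9 | 1–10% |
| 5 | 2.1–5.4 | 5–13% |
| 10 | 3.9–11.2 | 10–24% |

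**6. Validity.** With no treatment effect, simulated type I error without and with the covariate was 5.0% and 5.4% (q = 32%, p0 = 20%, ORz = 5), and 5.0% and 4.9% (q = 20%, p0 = 20%, ORz = 10). The simulation error is about 0.3 points.

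**7. What the imbalance clause leaves unadjusted.** With 151 per arm and 25% prior use (assumed), the SE of the between-arm difference in prior use is √(2·0.25·0.75/151) = 0.050. Gaps up to about 1.96 × 0.050 = 9.8 points are not statistically significant. If H6 risk were 40% with and 15% without prior use (assumed), such a gap would move the observed risk difference by 0.098 × 0.25 = 2.4 points.

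**8. What the composite hides.** With 20% prior use, two quite different patterns give the same rate:
- 20% initiation and 20% escalation: 0.8·0.20 + 0.2·0.20 = 20%.
- 10% initiation and 60% escalation: 0.8·0.10 + 0.2·0.60 = 20%.

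**The case against.** The strongest reply is that the plan already handles chance imbalance. SAP 6.4.3 and protocol 5.1.3 and 5.1.5 allow a variable that differs between arms to be added, and the H6 table would reveal a difference if shown by arm. So it would be wrong to infer that the plan ignores prior use. What stands against the reply is that the SAP route is conditional on the observed data and on a significance test. It is not a substitute for naming a prognostic covariate in advance.

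Four other stronger readings are not supported.
- **Bias or an invalid test.** Randomization protects the comparison, and step 6 shows the error rate is held either way.
- **The missing covariate causes the mixing of events.** The mixing comes from the endpoint definition. Adjustment alone would not separate initiation from escalation; only a breakdown does.
- **A large fixed loss.** The linear-scale formula R² = q(1−q)(pa−pb)²/[m(1−m)], with pa and pb the risks with and without prior use and m the overall risk, converts to 302·[1/(1−R²) − 1] infants. At q = 32%, risks of 50% v 10% give R² = 19.8%, about 74 infants; 20% v 15% give 0.4%, about 1. The answer is the assumption. Site and stabilization dose, already in the model, may also carry part of the signal.
- **Prior use is the strongest predictor, or belongs in H4 too.** Nothing in the documents shows either.

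It is also fair that SAP 6.4.2 foresees fewer covariates or Fisher's exact test if models fail, so another term has a cost when events are few.

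**Conclusion.** The point holds in a limited form. Prior second-/third-line drug use is collected and tabulated for H6 but not prespecified in its model, and the planned output does not split the two kinds of event. The H6 comparison remains valid.

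The efficiency at stake runs from nothing to about 11 points of power at N = 302. It depends wholly on an association that the documents do not give, and the top of the range needs a covariate odds ratio of 10. The gain is power for a conditional odds ratio; only on the risk-difference scale does the variance itself fall. The loss of interpretability does not depend on these assumptions.

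Importance is low to moderate: H6 is secondary, and SAP 6.4.4 treats every analysis other than the primary as exploratory.

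**What to change.** - In SAP 4.1 and 6.4.3, add use of a second-/third-line drug at the first weaning dose (yes/no) as a fixed covariate for H6.
- Define its derivation. The planned table covers drugs started before study drug, which could include a drug already stopped by the first weaning dose.
- State where this term ranks if covariates must be dropped under SAP 6.4.2.
- Report H6 by prior use and arm: initiation in infants not on such a drug, escalation or addition in those on one.
- Reconcile the escalation-only description in protocol 5.1.5 with the definition used elsewhere.
- Leave H4 as it is unless a separate case is made.

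The cost is a few lines of text, one derived variable and one extra table. Data on second- and third-line drug use are already collected, so no new data item should be needed, provided start and stop times allow status at the first weaning dose to be derived.
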